4.6.4 Biomarker Analyses

All PD analyses will be carried out using the safety-evaluable analysis population. The primary PD marker will be peripheral CD19-positive B cell counts. Total CD19-positive B-cell counts via MRB 1.1 and TBNK flow cytometry will be summarized graphically and

descriptively over time by treatment group. The absolute and percent change from baseline for each marker will be computed at each sampling timepoint. Additionally, the number and proportion of patients demonstrating B cell depletion per protocol definition (as defined in Section 5.1.1.7 of the protocol) will be summarized at each timepoint. For MRB1.1 based assessments, B cell depletion will be defined as <0.441 cells/ μ L (LLOQ of central lab assay). Counts of individual B cell subsets via BCP2.2 will be summarized graphically and descriptively over time by treatment group.] Additionally, the absolute and percent change from baseline for individual B cell subsets will be computed at each sampling timepoint.

Additional exploratory analyses may be performed to provide evidence of PD activity in circulation, urine and/or in tissues. These potential PD markers of B cell activity, inflammation, may include but are not limited to, B cell activation factor, anti-dsDNA, C3 and C4 complement. Percent and absolute change from baseline at each sampling timepoint for the above markers may be summarized graphically and descriptively as appropriate by treatment group.

Further exploratory analyses evaluating the possible relationships between biomarkers and clinical responses, safety, PK, or other biomarker endpoints maybe performed and will be defined in a separate biomarker analyses plan. Results of the biomarker analyses may be reported separately.

4.6.5 Health Status Utility Analyses

Change from baseline in EQ-5D-5L VAS scores will be summarized at Week 76. The questions will be summarized using proportions at Week 76.

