2.5 BIOMARKER OBJECTIVE

The PD objective for this study is to characterize the obinutuzumab-induced changes in circulating B-cells based on the following endpoint:

Total peripheral B-cell count at specified timepoints

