3.1.4 Study Follow-Up

Patients will be followed through Week 76 and for at least 12 months from the last dose of obinutuzumab or placebo:

- Patients who discontinue infusions prior to Week 76 will complete all visits through Week 76 according to the original schedule of activities before entering SFU.
- Patients who do not continue blinded infusions or enter open-label treatment based on the Week 76 assessment will enter SFU.
- Patients who discontinue all infusions (blinded and open-label) beyond Week 76 will enter SFU.

The first SFU visit will be scheduled approximately 6 months after the previous study visit (e.g., 6 months after Week 76). During SFU, patients will return for regular assessments every 6 months. Background immunosuppression, including MMF and corticosteroids, may be adjusted at the investigator's discretion. Obinutuzumab infusions will not be provided. Investigators and patients will not be unblinded to treatment assignment (except through emergency unblinding; see Section 4.2).

Those patients that have not reached B cell recovery, defined as peripheral CD19+ B-cell count at the lowest patient's pretreatment level or the lower limit of normal for the population under study, whichever is lowest, and who have not received a rescue therapy associated with reductions in peripheral B-cells (e.g., rituximab, cyclophosphamide, or use of obinutuzumab outside the study protocol) will continue to be followed every 6 months until any of the following occurs:

- Return of peripheral CD19+ B cells to the lowest pretreatment value or the lower limit of normal for this lupus population, whichever is lower
- Receipt of a therapy associated with reductions in peripheral B cells (e.g., rituximab or cyclophosphamide, or use of obinutuzumab outside the study protocol)
- Until end of study as outlined in Section 3.2

These represent the minimum required duration of follow-up for patients in the study. Investigators are encouraged to consider continuing SFU visits every 6 months until study unblinding occurs (see Section 3.1.5), at which point all patients who no longer require follow-up will complete the study.

After study unblinding has occurred (see Section 3.1.5), investigators may elect for patients to complete the study without completing the required 12 months of follow-up for the purpose of obtaining timely access to obinutuzumab infusions outside the study protocol (e.g., through the Sponsor's continued access provision, see Section 4.3.4).

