4.4.4 Rescue Therapy and Treatment Failure

4.4.4.1 Rescue Therapy

Disease flares may be managed with temporary increases in corticosteroid doses while continuing the study treatment regimen (see Appendix 5). In some cases of worsening or severely active disease, the investigator may conclude that the patient has failed the randomized treatment regimen and requires rescue therapy. The randomized treatment assignment will not be unblinded at the time of rescue therapy. Therapies that are considered rescue include the following:

- Cyclophosphamide
- Anti-CD20 antibodies, including rituximab, ocrelizumab, ofatumumab, and obinutuzumab (if given outside the study protocol)
- Calcineurin inhibitors including ciclosporin, tacrolimus, and voclosporin
- Other investigational, biologic, or targeted therapies used for the treatment of SLE or LN

Because these rescue therapies may affect subsequent efficacy assessments, patients who receive rescue will be treated as nonresponders for subsequent efficacy analyses.

Because the safety of obinutuzumab in combination with these rescue therapies has not been studied, patients who receive rescue will discontinue obinutuzumab or placebo infusions and will not be eligible for open-label treatment (see exception for corticosteroid-only rescue, Section 4.4.4.1.1 below). These patients will continue to be followed according to the study schedule of activities through Week 76 and for at least 12 months from the last dose of obinutuzumab or placebo (see Section 3.1.4).

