4.5 SAFETY ANALYSES

The safety analyses will be performed on the safety-evaluable population as defined in Section 3.1.3 with data collected in the Week 76 treatment period for each patient. Safety outputs will include data until the point of rescue for the patients who receive rescue therapy (excluding corticosteroid rescue). Limited key safety outputs will be produced for post-rescue data.

Safety data will be summarized by the obinutuzumab (combined treatment groups) and placebo groups. Additionally, combined obinutuzumab treatment group will be further broken down to obinutuzumab arm 1 (2-2-2 regimen) and obinutuzumab arm 2 (2-2-1 regimen) for selected key safety data up to Week 76.

Additional analysis including post Week 76 data collected till CCOD will be produced. The post Week 76 analysis details are provided in Section 4.6.7.

4.5.1 Extent of Exposure

A summary of exposure to study treatment will be produced using the dose recorded on the electronic Case Report Form (eCRF). The number of blinded obinutuzumab infusions and treatment duration will be summarized. Obinutuzumab treatment duration will be calculated as difference between date of last dose and date of first dose plus one day.

MMF exposure will be summarized using treatment duration and total cumulative dose.

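### SAP 4.6.4 has no cut at rescue for B-cell counts, so depletion caused by rescue drugs can enter the descriptive PD comparison between arms

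*SAP*

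**What the plan says.** Protocol 2.5 gives the aim: "The PD objective for this study is to characterize the obinutuzumab-induced changes in circulating B-cells". SAP 4.6.4 names the peripheral CD19-positive count as the primary PD marker and states "All PD analyses will be carried out using the safety-evaluable analysis population". Counts are to be shown graphically and "descriptively over time by treatment group", together with the number and proportion depleted at each visit and the B-cell subset counts. The section contains no rule on rescue.

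Elsewhere the SAP does have one. Section 4.5 says: "Safety outputs will include data until the point of rescue for the patients who receive rescue therapy (excluding corticosteroid rescue"), and adds "Limited key safety outputs will be produced for post-rescue data". The lymphocyte summaries in 4.5.3.3 (T-cell subsets and NK cells) fall under that section.

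SAP 3.1.3 defines the safety-evaluable population and groups patients by treatment received. Obinutuzumab given as rescue does not count as study treatment there, so it does not move a placebo patient into the obinutuzumab group.

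Protocol 4.4.4.1 lists cyclophosphamide, anti-CD20 antibodies (including off-protocol obinutuzumab), calcineurin inhibitors and other investigational, biologic or targeted drugs as rescue. Of rescued patients it says: "These patients will continue to be followed according to the study schedule of activities through Week 76". Protocol 3.1.4 ends extended B-cell follow-up on "Receipt of a therapy associated with reductions in peripheral B cells (e.g., rituximab or cyclophosphamide, or use of obinutuzumab outside the study protocol").

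**The concern.** The summary is meant to show what obinutuzumab does to B cells, but some rescue drugs act on the same cells. A placebo patient rescued with an anti-CD20 antibody stays on the visit schedule, has flow cytometry at later visits, and can be counted as depleted under placebo. The protocol itself recognises that such drugs lower B-cell counts, yet it uses that fact only to decide how long follow-up lasts.

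The handling is also uneven within one assay. T- and NK-cell counts stop at non-steroid rescue under SAP 4.5, whereas the CD19 count from the same tube is reported under 4.6.4, where no such stop applies. The marker most directly affected by anti-CD20 rescue is the one without the rule. At stake is a clean description of the PD effect, particularly at late visits, when more rescue will have accumulated.

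**Working it through.** **Does the plan, followed literally, let post-rescue counts in?**

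1. Counts will exist. Rescued patients follow the schedule to Week 76, and Protocol Appendix 1 (Table 1) has flow cytometry at Weeks 4, 12, 24, 36, 50 and 76.
2. Nothing removes them. SAP 4.6.4 refers to the safety-evaluable population, and the definition in SAP 3.1.3 includes patients without truncating their data. The cut in SAP 4.5 is written for safety outputs, whereas PD sits in 4.6 (Other Analyses).
3. Where the SAP wants a rescue cut outside 4.5, it writes one. The obinutuzumab arm of the All Exposure analysis (SAP 4.6.7) lists receipt of rescue therapy among its end points.
4. They can be counted as depleted. Protocol 5.1.1.7 defines depletion only by the assay limit, without regard to cause.
5. One assay, two rules. Protocol 4.5.5 lists B, T and NK cells under the TBNK assay. SAP 4.5.3.3 takes the T and NK counts, and SAP 4.6.4 takes CD19.

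**How large could it be?** The documents give no figure for placebo depletion, so there is none to reproduce. Inputs:

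- 126 planned patients on placebo (SAP 2.2).
- Phase II depletion on obinutuzumab at Week 52: 94% on conventional flow cytometry (Protocol 5.1.1.7) and 80% on the high-sensitivity assay (Protocol 1.3).
- Assumed, because the documents are silent: r, the share of placebo patients given non-steroid rescue before the visit, 2% to 20%; d, the share of those who are below the assay limit at the visit, 25% to 100%; p0, placebo depletion without rescue, 0.

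Apparent placebo depletion = r × d + (1 − r) × p0. The gap is the obinutuzumab rate minus this.

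| r | d | Placebo shown as depleted | Patients of 126 | Gap from 94% (points) | Gap from 80% (points) |
|---|---|---|---|---|---|
| 2% | 25% | 0.5% | 0.6 | 93.5 | 79.5 |
| 5% | 50% | 2.5% | 3.2 | 91.5 | 77.5 |
| 10% | 50% | 5.0% | 6.3 | 89.0 | 75.0 |
| 20% | 50% | 10.0% | 12.6 | 84.0 | 70.0 |
| 20% | 100% | 20.0% | 25.2 | 74.0 | 60.0 |

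With p0 = 2% the most extreme row becomes 0.20 × 1.00 + 0.80 × 0.02 = 21.6%. The gaps are then 72.4 and 58.4 points, against 92 and 78 without rescue.

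With data cut at rescue, placebo depletion returns to p0 among patients not yet rescued. Sample size, alpha and power for the primary endpoint are untouched.

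**The case against.** **Silence is not a decision.** No sentence says that post-rescue B-cell counts are kept. A reader might infer that the sponsor chose to keep them and that rescued placebo patients as a class will be counted as depleted. The documents support neither. Inclusion follows only from applying 4.6.4 as written. A rescued patient counts as depleted only if the drug depletes B cells and the count is below the assay limit at that visit. Calcineurin inhibitors and steroid-only rescue are not described as doing this. This objection limits the claim but does not remove it, because a programmer following the text would have no ground to exclude the samples.

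**Keeping the data is a legitimate choice.** SAP 4.3 uses a treatment policy strategy for rescue in the continuous secondary endpoints, including anti-dsDNA and C3, and 4.6.4 names both as possible PD markers. Cutting at rescue also removes treatment failures from late visits, which is selection related to outcome. Both points stand, and they are the reason for showing two displays.

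**The effect is small and works against the drug.** In the placebo arm it narrows the contrast, and the summary is descriptive and outside the alpha sequence. This stands.

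**Two further inferences are not supported.** One is that rescue would make depletion on obinutuzumab look durable. In Phase II, 94% were depleted at Week 52 after a last infusion at Week 26, so patients who stop may stay depleted from study drug alone. If that rate held, rescue could add at most 100 − 94 = 6 points on the conventional assay. The other is that the relation between depletion and response would be distorted. SAP 4.6.4 leaves biomarker-response analyses to a separate plan that is not available here.

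**Conclusion.** The point holds as a gap in the PD analysis rule. Followed as written, SAP 4.6.4 allows depletion due to rescue drugs to be shown under placebo, while SAP 4.5 stops the T- and NK-cell counts from the same assay at rescue. The consequence is dilution of a descriptive contrast, put illustratively at 0.5 to 20 points of the placebo arm. That range rests on assumed rescue rates and drug effects and on little or no placebo depletion without rescue. The gaps also assume that the Phase II depletion rates carry over to this trial. Even at the extreme the arms remain about 74 points apart on the conventional assay and 60 on the high-sensitivity assay, or 72.4 and 58.4 if 2% of unrescued placebo patients are depleted. A reader might fear that the PD conclusion itself is at risk, but these figures do not support that. It is a cheap improvement, not a threat to the trial's conclusions.

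**What to change.** Add to SAP 4.6.4 that CD19 counts, depletion status and B-cell subset counts will be summarised using data up to first non-steroid rescue, with the number of patients contributing at each visit, and that the same summary using all data will be shown alongside.

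First non-steroid rescue is the better cut point. It matches SAP 4.5 and uses the same flag. The drugs named in Protocol 3.1.4 are given only as examples, so they cannot define a data flag without further work.

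The cost is a sentence or two in the SAP and a second set of displays, with no new data. The downside is that rescued patients, who are treatment failures, leave the late-visit denominators, including some given drugs with no stated effect on B cells. The contributing numbers and the all-data display let the reader see what that does.

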5.1.1.2 Infections

Serious bacterial, fungal, and new or reactivated viral infections can occur during and following the completion of obinutuzumab therapy. Fatal infections have been reported.

Obinutuzumab is more potent in B-cell depletion than is rituximab. It is theoretically possible that there is an increased risk of infections with obinutuzumab compared with rituximab. Study BO21004/CLL11 provides the most meaningful assessment of the possible greater risk of infection (Goede et al. 2014). In Stage 1a (obinutuzumab+chlorambucil versus chlorambucil alone) and Stage 2 (obinutuzumab+chlorambucil versus rituximab+chlorambucil) of Study BO21004 in patients with CLL, the incidence of infections was similar between the treatment arms. However, the chlorambucil arm compared with the obinutuzumab+chlorambucil arm showed a higher incidence of serious infections and deaths due to infection; the incidence of serious infections and fatal infections was similar in the obinutuzumab+chlorambucil and rituximab+chlorambucil arms. To date, there is no clear evidence of a difference between rituximab and obinutuzumab regarding infections.

In the NOBILITY study at the Week 76 data cut, a higher incidence of infections (serious and non-serious) was observed with obinutuzumab compared to placebo (70% vs. 64%). However, the placebo arm showed higher incidences of Grade ≥3 infection (21.0% vs. 4.8%) and serious infections (17.7% vs. 6.3%) compared to the obinutuzumab arm. Through Week 104, the incidence of infections (serious and non-serious) was 75% vs. 62% with obinutuzumab and placebo, respectively.

Hepatitis B Reactivation

HBV reactivation, in some cases resulting in fulminant hepatitis, hepatic failure, and death, can occur in patients treated with anti-CD20 antibodies, including obinutuzumab in hematologic malignancies.

No cases of hepatitis B reactivation were observed in the NOBILITY study as of the Week 104 data cut.

Progressive Multifocal Leukoencephalopathy

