5.1.1.7 B-Cell Depletion and Recovery

B-cell depletion is defined as levels of peripheral CD19+ B cells below the TBNK assay limit of quantitation using conventional flow cytometry. B-cell recovery has taken place whenever peripheral B cells are no longer depleted and is defined as peripheral CD19+ count at the lowest patient's pretreatment level or the lower limit of normal for the population under study, whichever is lowest.

Obinutuzumab in Lupus Nephritis

In NOBILITY, obinutuzumab 1000 mg infusions at Day 1 and Weeks 2, 24, and 26 resulted in peripheral B-cell depletion of 94% of patients at Week 52. At the next measurement at Week 104, 16% of obinutuzumab patients were depleted to \leq 5 cells/ μ L.

Obinutuzumab Monotherapy: NHL and CLL Patients

In the Phase II part of study BO21003 (relapsed indolent NHL), 87 patients were included in the obinutuzumab arm and 86 in rituximab arm. The median level of CD19 cells was 0.079×10^9 cells/L at baseline and decreased rapidly to zero by 2.5 hours post-infusion on Cycle 1, Day 1. At the end of the treatment phase, of those with a known B-cell status, 80 of the rituximab patients (95%) and 82 of the obinutuzumab patients (96%) had B-cell depletion. At 18 months post-treatment, 5 of 8 and 17 of 19 patients (who were tested) in the rituximab and obinutuzumab arms, respectively, remained B-cell depleted.

The data from patients with NHL in Studies BO21003 and BO20999 were pooled and analyzed for B-cell depletion (a total of 205 patients). In this population from the pooled analysis, 195 of 202 patients (97%) had B-cell depletion at the end of treatment. At 12 months, 10 of 56 patients (18%) with known B-cell status had recovered B cells.

The data from patients with CLL in Studies BO21003 and BO20999 were pooled and analyzed for B-cell depletion (a total of 38 patients). In this CLL population from the pooled analysis, 30 of 35 patients with available data (86%) had B-cell depletion at the end of treatment. Twenty-seven of these patients had at least 6 months follow-up information (after the last study drug administration), and after 24 months, 19 of 27 patients (70%) had recovered B cells. Of note, there were no B-cell count data on the remaining 30% of patients as they had either progressed or died or were lost to follow-up before this timepoint.

Obinutuzumab in Combination with Chemotherapy: CLL Patients

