5.3.1 Adverse Event Reporting Period

Investigators will seek information on adverse events at each patient contact. All adverse events, whether reported by the patient or noted by study personnel, will be recorded in the patient's medical record and on the Adverse Event eCRF.

After informed consent has been obtained but prior to initiation of study drug, only serious adverse events caused by a protocol-mandated intervention (e.g., invasive procedures such as biopsies, discontinuation of medications) should be reported (see Section 5.4.2 for instructions for reporting serious adverse events).

After initiation of study drug, all adverse events will be reported until at least 12 months after the final dose of obinutuzumab or placebo. Additionally, for patients who require continued safety monitoring for continued B-cell depletion (see Section 3.1.4 for definition), adverse events will be reported until the earliest of the following occurs:

- Return of peripheral CD19+ B cells to the lowest pretreatment value or the lower limit of normal for this lupus population, whichever is lower
- Receipt of a therapy associated with reductions in peripheral B cells (e.g., rituximab or cyclophosphamide, or use of obinutuzumab outside the study protocol)
- Until end of study as defined in Section 3.2

Instructions for reporting adverse events that occur after the adverse event reporting period are provided in Section 5.6.

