6. STATISTICAL CONSIDERATIONS AND ANALYSIS PLAN

All efficacy outcomes will be analyzed using the efficacy-evaluable set that will include all randomized patients regardless of whether they received study treatment. Patients

will be grouped according to randomized (assigned) treatment, rather than treatment received.

Treatment period data will be locked after all patients have completed the Week 76 visit or discontinued from study. The primary efficacy and safety analyses will be performed on data for all patients through the Week 76 assessments or early study discontinuation. Further analyses will be performed once study unblinding occurs (see Section 3.1.5). Additionally, there will be a final safety analyses when all SFU is completed.

Safety assessments will be performed using safety-evaluable set defined as patients who have received any part of blinded infusion of obinutuzumab or placebo. In all safety analyses, patients will be grouped according to the treatment that patients actually received rather than the treatment assigned.

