6.4 SAFETY ANALYSES

The safety-evaluable population is defined as patients who received any part of blinded infusion of obinutuzumab or placebo. Patients who were randomized to the study but who did not receive any part of blinded infusion of obinutuzumab or placebo will not be included in the safety population. Patients will be grouped according to the treatment that patients actually received rather than the treatment assigned. Patients who received any part of an infusion of obinutuzumab even if not assigned to obinutuzumab treatment group at randomization will be reported under the obinutuzumab treatment group. All safety analyses will be performed using the safety-evaluable population.

Safety will be assessed through summaries of exposure to study treatment, adverse events, adverse events in relation to ADAs, adverse events in relation to B-cell depletion and low Ig, changes in laboratory test results, and changes in vital signs and ECGs.

Study treatment exposure (such as treatment duration, total dose received, and dose modifications) will be summarized with descriptive statistics.

All verbatim adverse event terms will be mapped to Medical Dictionary for Regulatory Activities (MedDRA) thesaurus terms, and adverse event severity will be graded according to NCI CTCAE v5.0. All adverse events, serious adverse events, adverse events leading to death, adverse events of special interest, and adverse events leading to study treatment discontinuation that occur on or after the first dose of study treatment (i.e., treatment-emergent adverse events) will be summarized by mapped term, appropriate thesaurus level, and severity grade. For events of varying severity, the highest grade will be used in the summaries. Deaths and cause of death will be summarized.

Relevant laboratory, vital sign (pulse rate, respiratory rate, blood pressure, pulse oximetry, and temperature), and ECG abnormalities will be displayed by time, with grades identified where appropriate. Additionally, a shift table of selected laboratory tests will be used to summarize the baseline and maximum postbaseline severity grade. Changes in vital signs will be summarized.

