The analysis will be based on post Week 76 blinded treatment efficacy-evaluable population as defined below.

Post Week 76 blinded treatment efficacy-evaluable population: Post Week 76 blinded treatment efficacy-evaluable population will consist of patients who continue blinded treatment period post Week 76 and reach at the specified endpoint assessment visits by CCOD. Patients enter the blinded treatment period, but later moved to OLT or SFU period or withdraw from the study prior to endpoint assessment, but would otherwise reach to the assessment visit by CCOD will be included. Patients will be grouped according to randomized (assigned) treatment, rather than treatment received. Patients

who received an incorrect therapy will be reported under the treatment group to which they were randomized.

4.6.7 All Exposure Safety Analyses including Post-Week 76 Data

In addition to the safety analyses detailed in Section 4.5, an All Exposure safety analysis will be performed including post Week 76 data from both blinded treatment and Open-Label Treatment (OLT) period.

The obinutuzumab arm of the All Exposure analysis will comprise of safety data from patients that received any dose of obinutuzumab. Patients that receive any dose of obinutuzumab, whether during the blinded treatment period or post Week 76 via OLT, will contribute safety data from their first dose of obinutuzumab until their last dose +6 months, the CCOD, study withdrawal or receipt of rescue therapy (whichever occurs first):

- Patients randomized to obinutuzumab at Day 1 who achieve adequate or inadequate response at the Week 76 primary analysis will continue to receive obinutuzumab (either blinded or open label). These patients will therefore contribute safety data to the obinutuzumab all exposure arm from their first dose at Day 1 following randomization.
- Patients randomized to placebo at Day 1 who achieve inadequate treatment response at Week 76 will switch to open label obinutuzumab treatment. These patients will therefore contribute safety data to the obinutuzumab all exposure arm following their first dose after switching to obinutuzumab treatment in the OLT period of the trial. Patients that switch from placebo to obinutuzumab will also be rebaselined as of their first dose of obinutuzumab during the OLT period.

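### The SAP specifies no summary of adverse events by B-cell depletion or low Ig, and its only safety window beyond Week 76 ends six months after the last dose, half the minimum collection period

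*SAP*

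**What the plan says.** **Protocol.** Section 6.4 names "adverse events in relation to B-cell depletion and low Ig" as one of the summaries through which safety will be assessed. Under section 5.3.1, once study drug has started, "all adverse events will be reported until at least 12 months after the final dose of obinutuzumab or placebo". Patients whose B cells have not recovered are followed beyond that, until recovery, a therapy that lowers B cells, or the end of the study. Section 6 adds that "there will be a final safety analyses when all SFU is completed".

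**SAP, outputs.** The adverse event list in 4.5.2 contains no table by B-cell depletion or Ig level. Section 4.5.3.2 gives low Ig by visit, and 4.6.4 gives B-cell depletion by timepoint. Neither is crossed with adverse events. On any link between the two, 4.6.4 says "Further exploratory analyses evaluating the possible relationships between biomarkers and clinical responses, safety, PK, or other biomarker endpoints maybe performed" and defers to a separate biomarker plan. Appendix 1, which records departures from protocol-planned analyses, lists only changed timepoints for exploratory renal response endpoints.

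**SAP, windows.** Section 4.5 runs the main safety analyses "with data collected in the Week 76 treatment period for each patient", cut at rescue other than corticosteroid rescue, with limited outputs after rescue. It sends later data to 4.6.7. There, patients given obinutuzumab "will contribute safety data from their first dose of obinutuzumab until their last dose +6 months", or to the clinical cutoff date, withdrawal or rescue if earlier. The placebo arm has the same six-month limit. No section of the SAP describes the final safety analysis.

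**The concern.** There are two gaps. The first is traceability: a summary that the protocol says will be produced has become optional in the SAP, and the document meant to record such changes does not mention it.

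The second is a stated rule. Followed as written, the six-month limit in 4.6.7 leaves out adverse events after Week 76 that the protocol requires sites to collect. It does so at a time when most patients given obinutuzumab can be expected to be still depleted. Protocol 5.1.1.2 warns of serious infections during and after treatment, and follow-up is extended specifically for patients without B-cell recovery. If the outputs stop at six months, the report cannot show whether infections continue while B cells stay low after dosing ends. That is the question the extended follow-up was set up to answer.

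**Working it through.** **1. Protocol summary against SAP outputs.** The promised summary crosses adverse events with depletion and with low Ig. The SAP has each ingredient separately: adverse events (4.5.2), low Ig by visit (4.5.3.2) and depletion by timepoint (4.6.4). It has no crossed table, no firm commitment to one, and no entry in Appendix 1.

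**2. Length of the window.** Inputs: the 4.6.7 limit is 6 months (26 weeks) after the last dose. The 5.3.1 minimum is 12 months (52 weeks). Protocol 3.2 sets a maximum of 18 months (78 weeks) from the last infusion.

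- Share of post-dose collection outside the 4.6.7 window: 1 − 6/12 = 50% at the minimum and 1 − 6/18 = 67% at the maximum.

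**3. A patient last dosed at Week 52 who enters follow-up after Week 76.**

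| Event | Arithmetic | Study week |
|---|---|---|
| 4.6.7 window closes | 52 + 26 | 78 |
| First follow-up visit (about 6 months after Week 76) | 76 + 26 | 102 |
| Minimum collection ends | 52 + 52 | 104 |
| Maximum collection ends | 52 + 78 | 130 |

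SAP 4.5 covers this patient to Week 76. Required collection beyond that is 104 − 76 = 28 weeks, of which 78 − 76 = 2 fall inside the 4.6.7 window. The first follow-up visit already lies outside it.

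**4. B-cell state when the window closes.** The Phase II regimen, with its last infusion at Week 26, "resulted in peripheral B-cell depletion of 94% of patients at Week 52". That is 52 − 26 = 26 weeks after the last dose, or 26 × 7/30.44 = 5.98 months, which is the 4.6.7 limit. No counts are given, so the 94% can be located but not recomputed. It is the conventional-assay figure. Protocol 1.3 gives 80% at the same time on the high-sensitivity assay. At Week 104, 104 − 26 = 78 weeks after the last dose, the figures were 16% (at or below 5 cells/µL) and 8% (high-sensitivity assay). Most recovery in Phase II therefore happened after the point at which 4.6.7 stops counting.

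**The case against.** **Later events do have a planned analysis.** A reader might infer that adverse events more than six months after the last dose appear in no output at all. The documents do not support that. Protocol section 6 promises a final safety analysis, protocol 6.4 summarises treatment-emergent events without a six-month stop, and SAP 4.5.2 defines treatment-emergent through study completion. This stands. What remains is that the SAP never specifies the final analysis and that its only stated post-Week 76 rule excludes these events.

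**Early stoppers.** The 50% figure does not apply to everyone. Patients who stop infusions early are counted to Week 76 under SAP 4.5 even when that is more than six months after their last dose, apart from post-rescue data. Responders and open-label patients are dosed every six months, so their window moves forward with each dose.

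**Unseen documents.** SAP 4.5.2 refers adverse event outputs to a List of Planned Outputs, and 4.6.4 refers to a biomarker plan. Either may contain the missing table. The gap is shown only for the SAP.

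**Phase II infections.** It is tempting to cite the widening difference as a signal that the window would miss. At the Week 76 cut infections were 70% vs 64%, a difference of 6 points. "Through Week 104, the incidence of infections (serious and non-serious) was 75% vs. 62% with obinutuzumab and placebo", a difference of 13 points. This cannot carry weight. With about 63 and 62 patients (inferred from the percentages), the standard error is √(0.75 × 0.25/63 + 0.62 × 0.38/62) = 0.082, so the 95% interval is about −3 to 29 points. The placebo figure falls between cuts, so the two do not share one base. Serious infections at Week 76 were lower on obinutuzumab (6.3% vs 17.7%). Nor would these rules have stopped Phase II data at Week 52, because SAP 4.5 would have covered every patient to Week 76.

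**Low Ig does not need the longer window.** In Phase II it already varied at Week 76 (IgM 38.6% vs 10.2%, IgG 10.5% vs 8.2%). That half of the protocol summary is feasible within the main window, which makes its absence easier to repair.

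**Safety biomarkers.** Protocol 5.3.5.14 keeps safety biomarker data out of the formal safety analyses. Protocol 6.4 nevertheless names this summary, and the SAP places Ig under its safety analyses.

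**Confounding.** Patients entering follow-up after Week 76 include primary nonresponders, rescued patients and those stopped for adverse events, all on investigator-chosen therapy. This limits interpretation. It does not justify leaving the data unspecified.

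**Conclusion.** The point holds, and it should be corrected before the final safety analysis. The SAP does not carry over a summary to which the protocol commits, and it does not record the change. Its one post-Week 76 safety rule ends at half the minimum collection period. For a last dose at Week 52 followed by study follow-up, about 26 of the 28 required weeks after Week 76 lie outside it, at a time when 80% to 94% of Phase II patients (depending on the assay) were still depleted.

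This assumes that depletion in this trial resembles Phase II, although the regimen here adds infusions at about 12 months. It also assumes that the List of Planned Outputs and the biomarker plan do not already cover the gap, which could not be checked. The documents do not show that later events will go unreported, or that obinutuzumab raises late infections. Efficacy tests are unaffected, and so are the adverse event tables already planned through Week 76.

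**What to change.** Keep the existing 4.6.7 analysis and make two additions.

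1. **In SAP 4.6.7, as the content of the final safety analysis:** adverse events, serious adverse events, infections, serious infections and events of special interest over the full protocol 5.3.1 reporting period. Give rates per 100 patient-years, split at 6 months after the last dose, and stop at rescue or another B-cell-depleting therapy.
2. **In SAP 4.5.2:** the protocol 6.4 descriptive summary of adverse events and infections by B-cell depletion (yes or no at the last sample before onset) and by low IgG. If this is no longer intended, list its removal in Appendix 1.

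A finer grid of time bands by several B-cell states is not needed, and the protocol does not ask for one.

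**Cost:** SAP wording and two descriptive tables. Adverse events, flow cytometry and Ig are already scheduled at follow-up Weeks 0, 26 and 52 and later (protocol Appendix 1, Table 4), so no new data are needed. Six-monthly sampling makes B-cell state at onset approximate. Late follow-up comes from a selected group on varied background therapy, so the tables should carry that caution.
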